## 493 2.3.1 Primary Outcome Variable

Our primary outcome is the completion of fecal testing within the earlier of (a) 12 months from study
accrual or (b) August 3, 2015 (when study tools were made available to usual care clinics). As our primary
interest was on clinic level return rates, however, these individual responses were weighted by 1/(clinic
size) so that each clinic's data was weighted equally (see section 2.4.1).

498

510

511

512

513

514

515

516

517

To assure maximum comparability of the intervention and control samples, all participants were accrued in the same manner. For control clinics we thus looked for the first date that a participant would have been eligible to receive the intervention had it been turned on for that site. It follows that both the distribution of accrual times as well as the distribution of follow up times should be comparable for participants in the two groups.

## 505 2.3.2 Secondary Outcomes

[figure not shown]
- 506 Our secondary outcomes are provided below:
- For participants who received a FIT kit, the probability of returning it within 3, 6, 9 and 12 months of its being sent as well as time to FIT/FOBT return
   Receipt of any CRC screening (fecal test, sigmoidoscopy or colonoscopy) during the follow-
  - NQF score (proportion of those age 50-74 with a colonoscopy within 10 years, flexible
  - sigmoidoscopy within 5 years, and FOBT/FIT within 1 year) as assessed relative to the oneyear pre and each of the first two years post randomization
    - Presence of a positive FIT/FOBT among those who return a FIT kit
    - Referral for a colonoscopy among those with a positive FIT/FOBT
    - Completion of a colonoscopy following a positive FIT/FOBT

## 518 **2.3.3. Process Outcomes**

519 Though not secondary outcomes per se, we will also record a number of process measures that describe

520 the Reach, Adoption, and Implementation of the intervention among intervention clinics. These are

521	summarized below:
522	
 
Adoption: N clinics that participate/ N anticipated [characteristics of adopters]
 

523 524 525	
 
Reach: N participants who receive intervention components / N anticipated. We will record N invalid address, N decline, and N who report prior screening. We will also assess patient phenotype characteristics related to reach (e.g. such as race, language and invalid address)
 

526	
 
Implementation: N activities delivered by clinics / N anticipated.
 

527 528 529 530 531	
 
Maintenance: N clinics that implement STOP CRC in YR 02/ N implemented in YR 01. For those clinics who do adopt/maintain the intervention in year 2, we will describe similar intervention outcomes for year 2 (e.g., percent with FIT/FOBT returned within 12 months) and the proportion of eligible patients current for FOBT and any CRC screening for both years of the study.
 

532 533 534	
 
In addition to the measures above, we will gather qualitative data to assess the adoption and fidelity of implementation of the program in the clinics; including clinic-level barriers to ongoing maintenance and patient-level factors that influence program effectiveness.
 

535 536	
 
As this is a stepwise intervention, the reach and implementation for each component will be based on the number eligible for that step.
 

537	• The following variables will be captured in Reporting Workbench:
538	
 
Intro letter mailed, date
 

539	
 
Income phone call, date
 

540	
 
Declined participation, date
 

541	
 
Reported previous CRC screening, ineligible, date
 

542	
 
Invalid address, date
 

543	
 
FIT kit mailed, date
 

544	
 
Requested new kit, date
 

545	
 
Postcard mailed, date
 

546	Samples of project reports are available in Section 4: Research Reports.
547 548	2.3.4. Assessment of adoption
549 550 551 552 553 554	From the original list of 41 Health Centers in Washington, Oregon and Northern California, 13 Health Centers had a single clinic or did not meet the size requirements of having at least 2 clinics with 450 patients aged 50-74, and 17 were outside of the geographic catchment area. The remaining 11 Health Centers were eligible and 3 declined participation. Among the recruited clinics, 24 were FQHCs with shared governance (a centralized leadership team, etc.) and 2 clinics were affiliated with an academic medical center (and operated independently of each other). To assess adoption, we will:
555 556	
 
Compare and report clinic characteristics of adopters and non-adopter; these include clinic size, location, % Hispanic, % uninsured, and baseline CRC screening rates, among others.
 

557 558	• For our assessment of maintenance, we will also track and report clinics that decline participation in YR02.
559 560	Figure 5, below, shows the CONSORT diagram of clinic recruitment. A-19

#### Figure 5: Clinic-level CONSORT diagram for STOP CRC

## 562

#### 563 2.3.5. Moderator Variables

564 Moderators include demographic characteristics, health status, and health care utilization variables. The 565 following variables will be assessed as moderators of the intervention.

- Demographic characteristics will be assessed using the following variables:
- 567

566

568

569

574

575

576

- Age, on date of first mailing [50-64, 65-75]
- Gender [Female, Male]
  - Race, self-reported [Black, Asian, While, Native American, Unknown]
- 570 Ethnicity [Hispanic, non-Hispanic]
- 571 o Language, primary self-declared [English, Spanish, other]
- 572 Tobacco use, at last visit [Current, Passive, Never, Unknown]
- 573 Socio-economic status [<100% FPL, 100-150 FPL, 151-200 FPL, 200+ FPL]
  - Insurance status [Uninsured, Medicaid, Medicare, Private, Other]
    - Community- and neighborhood-level variables obtained from linking EHR to Census and American Community Survey data.
- Health care utilization will be assessed using ACG or Charlson Risk Scores if possible, or the following variables:
  - History of FIT/FOBT, among aged 52-74 prior to exclusion period [Yes, No]]

580	• History of Pap screening, among women aged 50-64, in past 3 years [Yes, No]
581 582	
 
History of mammography screening, among women aged 50-74, in past 2 years [Yes, No]
 

583	
 
Flu shot in past year, both genders, all aged 50-74 [Yes, No]
 

584	
 
Number of office visits in past year [continuous N]
 

585	
 
Number of office visits during intervention year [continuous N]
 

586 587	
 
We will consider as moderators health status and co-morbid conditions using the following variables:
 

588	
 
Congestive heart failure (CHF), ever
 

589	
 
Peripheral vascular disease (PVD), ever
 

590	
 
Cerebral vascular disease/ dementia, ever
 

591	
 
Chronic obstructive pulmonary disease, ever
 

592	
 
Diabetes mellitus (exclude gestational diabetes), ever
 

593	
 
Metastatic solid tumor, ever
 

594	
 
Hypertension diagnosis, ever
 

595	
 
Depression diagnosis, ever
 

596	
 
Currently using Warfarin
 

597	
 
John Hopkins Adjusted Clinical Group (ACG) case-mix system comorbidity score
 

598	

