#### 412 **1.12** Selection of Eligible Patients

413 The main eligibility criteria for STOP CRC are screening criteria as adopted by the National Quality Forum (NQF).

Patients must be 50-74 years old, an active patient identified by a prior visit, without screening or conditions that

415 would make them poor candidates for screening. Below is a list of the inclusion and exclusion criteria for the 416 project.

Inclusion and Exclusion Criteria for STOP CRC Patient Participants	Time	Temporary/Permanent**
Inclusions		
Aged 50-74	Current	Temporary
Have at least 1 visit in past 12 months	Past 12 months	Temporary
Have viable address	Current	Temporary
Exclusions – CRC screening history		
Colonoscopy Complete	Past 9 years	Temporary
Colonoscopy Referral	Past 1 year	Temporary
Gastroenterology Referral	Past 1 year	Temporary
FIT (or FOBT) Orders	Past 11 months	Temporary
Flex sigmoidoscopy Referral	Past 1 year	Temporary
Flex sigmoidoscopy Complete	Past 4 years	Temporary
Exclusions – Colorectal disease		
Prior dx of colorectal cancer	Ever	Permanent
Prior dx of total colectomy	Ever	Permanent
Ulcerative colitis and Inflammatory Colitis	Ever	Permanent

History of high risk polyps –	Ever	Permanent
Exclusions: co-morbid conditions		
History of renal failure/ESRD	Ever	Permanent
Living in nursing home or assisted living	Past 1 year	Temporary
Hospice Program	Ever	Permanent

\*Additional local codes should be included in procedures list if available.

419 \*\*Temporary means that status can change during observation period.

420

421 The tables below list the codes that were used to identify colonoscopy orders, results and GI referrals, FIT/FOBT orders, flexible sigmoidoscopy referrals and completions, colorectal disease, and co-morbid

422 conditions.

423

424

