## 690 **2.5. Power and Sample Size**

For Phase 2, STOP effectiveness will be assessed using a two-arm, cluster randomized design with a total of26 clinics. Our power calculations are based on the following assumptions:

- We have equal Ns per clinic and equal numbers of clinics per group. In practice, the sample sizes will not be equal, but since almost all clinics had at least 450 subjects who qualified for the intervention (most had at least 700 qualifying individuals), we conservatively use this figure for all sites.
- We compare two binomial proportions with a type I error rate of 5%. For each of a variety of
   design assumptions, we determined the design effect due to clustering and used this to calculate
   the effective sample size as if these were independent observations. We then used the formulas
   from Hulley et al., to estimate power.
- Finally, we assume an intention-to-treat approach in which we consider a treatment failure to be any individual who receives the initial intervention mailing (or for the UC clinics would have qualified to receive the mailing) and does not have a completed fecal test within their follow-up window. Although we expect to learn through the intervention process that many intervention participants do not require screening, we have no way to exclude comparable individuals from the control clinics and hence must ignore this information for the primary analysis.
- 709
  710 We calculated power for Intra-class Correlation Coefficients (ICCs) of .03, .04, and .05, usual care FIT return
  711 probabilities of 5%, 10%, and 15%, and intervention effects (absolute differences) of 10 14 percentage

- points. Based on analyses done by [name] (STOP co-PI), we expected the ICC to be about .03, though as
  it turned out the ICC was closer to .05. Using this latter figure, we had >90% power for detecting effect
  sizes of at least 13 percentage points even with UC probabilities as high as 15%. Power was > 88% for
  detecting effect sizes of at least 11 percentage points if the UC probabilities were no higher than 10%.
  Power declines only slightly even for subgroups 1/6th of the full cohort (e.g., for 17% Hispanic patients).
- 717 This reflects the fact that we have an overabundance of individuals within each clinic and that the main
- 718 driver of power is thus the number of clinics.
- 719

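### Office visits during the intervention year are listed as a moderator, but they are counted after randomization, so the arm-by-visits interaction is not a clean test of effect modification

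*Protocol*

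**What the plan says.** Section 2.3.5 opens by stating that the "following variables will be assessed as moderators of the intervention". The utilization block is introduced conditionally: "Health care utilization will be assessed using ACG or Charlson Risk Scores if possible, or the following variables". Two visit counts stand next to each other in that block, "Number of office visits in past year [continuous N" and "Number of office visits during intervention year [continuous N". The first looks back; the second covers the intervention period.

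Section 2.4.3 plans a detailed moderator analysis of patient-level factors with random effects models. Section 2.3.1 ends each patient's outcome window at the earlier of 12 months from accrual or August 3, 2015.

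Age is listed in section 2.3.5 as "Age, on date of first mailing [50-64, 65-75". Section 1.12 sets eligibility: "Patients must be 50-74 years old, an active patient identified by a prior visit".

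**The concern.** A moderator should be fixed before the intervention can act on it. Otherwise a difference in effect across its levels may reflect what the intervention, or the outcome, did to the variable. Visits in the intervention year do not meet that condition:

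- **Intervention to visits and outcome.** Section 1.4 says the provider can see that a kit was mailed and can remind the patient at a clinic visit to return it. Visits are thus part of how the mailing is expected to work.
- **Outcome to visits.** Section 2.3.2 follows positive tests through referral to colonoscopy. Section 2.3.5 does not limit the count to visits before test completion, so visits that follow a test can enter it.
- **Difference between arms.** Intervention patients can complete a test from a mailed kit without attending. The study gave usual care clinics no such route before August 2015, so the link between attending and being tested may well differ by arm.

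A spurious interaction could lead readers to conclude that the program works better or worse for frequent attenders. The count is also unknown when a kit is mailed, so it could not guide whom to mail.

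**Working it through.** The protocol states no figure for the moderator analysis, so there is nothing to reproduce. The check is one of timing, followed by two illustrations whose inputs are assumptions.

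**Timing.** Randomization was on February 4, 2014 (section 2.2). Accrual ran to February 3, 2015, with a common cut-off of August 3, 2015 (sections 2.3 and 2.3.1). Outcome windows are therefore 12 months for patients accrued by August 3, 2014, falling to 6 months for those accrued last. Visits during the intervention year fall in the same period as the outcome. The past-year count can be taken before accrual, and section 1.12 requires at least one visit in the past 12 months, so it exists for every patient in both arms.

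**Illustration 1: can a false interaction arise?** Logistic simulation, 400,000 patients, no true effect modification. The quantity is the arm-by-visits interaction odds ratio per visit, which should be 1. Standard error is about 0.004.

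| Visit count used | Extra visit among test completers | Interaction OR per visit |
|---|---|---|
| Past year | not applicable | 0.997 |
| Intervention year | none; unaffected by arm or outcome | 0.996 |
| Intervention year | 10% in both arms | 0.997 |
| Intervention year | 30% usual care, 10% intervention | 0.958 |
| Intervention year | 100% usual care, 10% intervention | 0.838 |

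The first three rows are within simulation error of 1. The fourth is off by 1 − 0.958 = 0.042, about ten standard errors. Compounded over a difference of four visits, the last two rows give 0.958^4 = 0.84 and 0.838^4 = 0.49. Bias therefore requires outcome-linked visits that differ by arm; a post-randomization count alone does not guarantee it. The percentages in the table are assumptions, and the documents give none.

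**Illustration 2: does the dating of age matter?** Assume ages uniform over 50 to 75, a span of 25 years. Dating age t months later moves a share (t/12)/25 across the 65-year cut:

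- t = 4 (accrual in February 2014, first letters in June 2014): 0.333/25 = 1.3%
- t = 12: 1/25 = 4.0%
- t = 18 (February 2014 to August 2015): 1.5/25 = 6.0%

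This would arise if actual mailing dates were used in one arm and eligibility dates in the other. Section 2.4.1 notes that no clinic printed letters before June 2014 and that some began only in spring 2015.

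**The case against.** **The item is conditional.** The visit counts apply only if ACG or Charlson scores are not possible, so this one may never be used. That limits the exposure but does not remove the fault, because the variable is live whenever the fallback is. The ACG score also appears separately in the health status list of the same section, so when the fallback applies is not entirely clear.

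**Bias is not certain.** This stands. The simulation shows none when visits are unaffected, or respond equally in both arms. The most that can be said is that the estimate may be biased.

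**An odds ratio gradient would not prove the point.** A reader might infer moderation, or bias, from an odds ratio that falls as visits rise. Suppose each visit gives a 4% chance of a test in both arms and mailing adds an independent 7% chance. Completion is then 4.0% versus 10.7% at one visit (odds ratio 2.9) and 18.5% versus 24.2% at five (odds ratio 1.4). The risk differences, 6.7 and 5.7 points, are similar. The gradient comes from the odds ratio scale, and a baseline visit count would show the same pattern.

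**Age can be computed.** A reader might infer that dating age at first mailing makes the variable uncomputable or drops the control arm. The documents do not support this. Section 2.3.1 supplies an index date: "For control clinics we thus looked for the first date that a participant would have been" eligible for the intervention. Section 2.5 uses the same analogue, "or for the UC clinics would have qualified to receive the mailing", and the primary model in section 2.4.1 adjusts for age in both arms. The 65-75 band is not an error either, since a patient accrued at 74 can be 75 by a delayed mailing.

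**The link to Primary Aim 1 is limited.** Its example subgroups are age, sex, insurance and Hispanic ethnicity/race. Visit counts are not among them.

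**Conclusion.** The point holds in a limited form. One listed moderator is measured after randomization, over the outcome window, and may be affected by assignment or outcome. Its interaction with arm is not a clean test of moderation. The size and direction of any bias cannot be derived from the documents; both depend on how outcome-linked visits differ between arms. Such a difference is plausible from the design but is not quantified. The random effects models of section 2.4.3 do not resolve this, because the difficulty lies in when the variable is measured.

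The age item is a loosely worded reference date: a first mailing has no literal value in usual care, and section 2.3.5 does not point to the accrual date. Under the uniform-age assumption, about 1% to 6% of patients would change band.

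Both matters concern moderator analyses only. The primary analysis is unaffected.

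**What to change.** In section 2.3.5, delete the intervention-year visit count from the moderators, or keep it under a separate label as a descriptive post-randomization variable with no interaction test. Retain the past-year count and state that it covers the 12 months before the accrual date.

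As a minor companion change, date age at the accrual (first-eligibility) date of section 2.3.1 in both arms. With that date, the eligibility limits imply an upper band of 65-74.

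The cost is a wording change. The replacement visit count is already on the list, and the accrual date is already defined for both arms. If the interaction with intervention-year visits has already been fitted, report it as descriptive and say why.

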### 599 2.4 Analysis

The original analytic plan called for aggregating each clinic's data into 8 separate return rates (one each for subgroup defined by age (50-64 vs. 65+), gender and race (minority vs. non-minority). The resulting analytic dataset would thus consist of 208 observations (26 clinics X 8 observations per clinic). Treating the resulting proportions as approximately normally distributed, we planned to use mixed model ANCOVA to estimate the screening probabilities as a function of intervention, age, gender, race, and baseline clinic screening rate, with clinic specified as a cluster variable.

- 606 607 Once the analytic cohort was accrued, we discovered that some of the clinic subgroups were extremely 608 small, which in turned threatened the validity of the planned analysis. In consultation with the NIH 609 Collaboratory's Biostatistics Core, we therefore shifted to a patient level analysis. In order to maintain the 610 initial focus on clinic-level differences, we weighted each individual by 1/(clinic size). This shift in analytic 611 plan therefore maintained the spirit of the original analysis while providing a better fit to the nature of the 612 data (i.e., a logistic model reflecting the binary nature of individual observations). An added bonus of this 613 revised analytic framework is that it allowed for a finer adjustment for patient-level factors as part of 614 secondary analyses.
- 615
- 616 In addition to the above change, we also added some sensitivity analyses to try to account for the startup
- 617 delays that were experienced. Finally, we decided to adjust for Health Center in place of other clinic-level
- 618 covariates since preliminary analyses indicated that this substantially reduced the intraclass correlation
- 619 coefficient compared to other adjustment options.

625

### 621 **2.4.1** Primary and Secondary Outcome Analysis

The data can be viewed as coming from a 2-level hierarchical model with patients clustered within clinics,
and our primary interest is focused on clinic-level effects (to what extent did the intervention increase
clinic-level FIT/FOBT completion rates).

626 Primary Analysis

627 To assess our primary outcome, we fit generalized estimating equations (GEE) models with a logistic link to 628 model patient-level data. Patients are weighted by 1/(clinic size), so that each clinic's data will have an 629 equal weight. The primary analytic model adjusted for age, gender and health center, used robust variance 630 estimators, and specified clinic as a clustering variable to account for intra-clinic correlation. (The intra-631 class correlation coefficient for this adjusted model was 0.05.) We report the intervention effect as the 632 absolute difference between intervention and usual care clinics in adjusted probabilities calculated using 633 mean values for all covariates in the model since we felt this was the more relevant metric from a public 634 health perspective. However, we report (two-sided) p-values based on the ln (odds ratio). A p-vlaue < 0.05 635 is considered statistically significant.

636

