
#### 386 1.11 Participating clinics

387 STOP CRC will work with several OCHIN-affiliated clinics in Oregon and California. In later years, we will
 388 adapt and pilot-test the program at Sea Mar Community Health Centers. Below is a list of participating

389 clinics organizations, and the number of eligible and participating sites.

 

Clinic Organization	Number of clinic sites with 450+ active patients	Number of participating clinics
Health Center 1	2	2
Health Center 2	3	3
Health Center 3	3	3
Health Center 4	4	4
Health Center 5	6	6
Health Center 6	2	2
Health Center 7	6	4
Health Center 8	4	2

#### 391

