### 476 **2.2. Randomization**

477 Based on simulation work conducted by the Collaboratory's Biostatistics Core, we abandoned our original

478 plans to conduct a constrained randomization and instead opted for a simple stratified randomization

based on Health Center. Within each of these administrative units, the randomization was blocked to

480 assure maximum possible balance of intervention and control clinics. Having created the basic

- randomization scheme with two groups (A and B), the assignment of the groups to intervention and control
- 482 conditions was performed randomly on a conference call with all health center representatives on February
- 4th, 2014 to assure maximum transparency of the process to our participating sites. The randomization
   process relied on an electronic dice that was rolled by a member of the advisory board.
- 485

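### The primary GEE test names robust variance but no small-sample correction for 26 clinics in 8 Health Centers; on its ordinary reading, type I error is about 12-15% rather than 5%

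*Protocol*

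**What the plan says.** Section 2.4.1 of the Protocol, in the chapter titled Statistical Analysis Plan, sets out the primary test. It is a logistic GEE on patient-level data with clinic as the clustering variable. On weights: "Patients are weighted by 1/(clinic size), so that each clinic's data will have an" equal weight. On covariates and variance: "The primary analytic model adjusted for age, gender and health center, used robust variance" estimators. On the test: "However, we report (two-sided) p-values based on the ln (odds ratio). A p-vlaue < 0.05" counts as significant. The adjusted model's ICC is given as 0.05.

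Section 2.4 explains the center adjustment: "we decided to adjust for Health Center in place of other clinic-level" covariates, because preliminary analyses showed that this lowered the ICC. Section 2.2 says the trial "instead opted for a simple stratified randomization" by Health Center, blocked within center. On the number of centers, section 2.3.4 says: "The remaining 11 Health Centers were eligible and 3 declined participation", which leaves 8. The table in section 1.11 runs to "Health Center 8" and lists 2, 3, 3, 4, 6, 2, 4 and 2 participating clinics.

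Section 2.4.1 applies the same approach to any CRC screening. Its sensitivity models drop the weights, add insurance status, use random effects, or exclude the two academic clinics. None is described as a small-sample correction.

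**The concern.** A sandwich variance is built from cluster residuals. With few clusters and several cluster-level terms, the fit pulls those residuals toward zero and the variance comes out too small. Here the intercept, the arm and seven center indicators use 9 of 26 clinic-level degrees of freedom. Three centers have only two clinics and two have three, so individual clinics have high leverage. Section 2.4 weighs the gain in ICC from adjusting for center but not this cost.

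At stake is the p-value for the primary outcome and any interval built on the same standard error. The same applies to any CRC screening and to the GEE sensitivity models.

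**Working it through.** **Inputs from the Protocol.** Clinics: 2+3+3+4+6+2+4+2 = 26, in 8 centers (section 1.11). Two-sided alpha 0.05 and adjusted ICC 0.05 (section 2.4.1). Usual-care rates of 5-15%, ICCs of .03-.05 and 450 patients per clinic (section 2.5).

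**Assumptions.** Health Center enters as seven indicators; working independence; clinic-level sandwich; Wald test on ln(OR). The spread of clinic sizes is not given, so it was varied.

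**The plan's own figures.** The figure at issue is the nominal 5%. The power table in section 2.5 comes from a two-proportion formula with a design effect, not from this GEE test, so it neither supports nor contradicts the point. It reproduces within 0.4 points in all 45 cells with 12 clinics per arm, 450 patients each and a continuity correction. With 13 per arm and that correction, 9 of 45 cells are more than 2 points off. That does not affect what follows.

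**Step 1, degrees of freedom.** 26 − 1 (intercept) − 7 (centers) − 1 (arm) = 17.

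**Step 2, closed-form approximation.** With equally weighted clinics the uncorrected variance is about 17/26 = 0.654 of the true variance.
- Normal reference: P(|t17| > 1.96 × √(17/26)) = P(|t17| > 1.585) = 13.1%.
- t reference alone: P(|t17| > 2.110 × √(17/26)) = 10.6%.

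**Step 3, normal clinic-level simulation in the actual layout (40,000 draws).** Least squares with t on 17 df rejects 5.2%, so the set-up is calibrated. The uncorrected sandwich with z rejects 13.5%, and with t17 10.9%. Without the center terms the sandwich with z rejects 7.3%, so the center terms account for most of the excess.

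**Step 4, logistic GEE simulation under no effect.** Blocked randomization within center and beta-binomial clinic rates, 2,500 runs per row shown (Monte Carlo SE about 0.4-0.7 points).

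| Setting | Sandwich, z | Sandwich, t17 | Kauermann-Carroll, t17 | Robust / true variance |
|---|---|---|---|---|
| 450 per clinic, UC 15%, ICC .03 | 13.6% | 11.0% | 5.4% | 0.64 |
| 450 per clinic, UC 15%, ICC .05 | 13.5% | 10.7% | 5.3% | 0.64 |
| Unequal sizes (assumed lognormal, median 1,200), UC 10%, ICC .05 | 15.0% | 12.4% | 6.0% | 0.60 |
| Age and gender added, UC 10%, ICC .05 | 15.4% | 11.9% | 5.2% | 0.60 |
| Assumed ICC .01, UC 10% | 12.2% | 9.3% | 4.0% | 0.69 |

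Across usual-care rates of 5-15% and ICCs of .03-.05 with 450 per clinic, the sandwich with z gives 13.5-14.4%. A G/(G−1) factor with z changes little: 11.2-14.2% over all settings. Mancl-DeRouen with t17 is conservative, at about 2%.

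**Step 5, a different data model.** With logit-normal clinic effects and assumed sizes of 450-2,500, the sandwich with z gave 14.0-15.2% at usual-care rates of 10-15%, and Kauermann-Carroll with t17 gave 5.8-6.8%. At a usual-care rate of 5% and ICC .05 the sandwich with z reached 17.5%. That single result depends on the assumed size spread and is not relied on.

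**The case against.** The strongest objection is that the Protocol never says the variance is uncorrected. Robust variance does not exclude a bias-corrected estimator or a t reference, and software settings of this kind are often left to a separate document. This stands as a limit on the claim: with a correction and t17 the rate is near 5%, and nothing here shows what was actually run. It does not dispose of the point. The chapter is itself the analysis plan, it specifies the test down to sidedness and threshold, and the ordinary meaning of its words does not deliver the stated 5%.

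Three stronger readings are tempting and should be resisted.
- A reader might infer that the trial's true false-positive rate is 14-15%. That is the upper part of a conditional range which depends on the ICC, clinic sizes, reference distribution and coding of Health Center.
- A reader might call this the trial's only confirmatory p-value. The Protocol does not say so.
- A reader might infer from the reported ICC that an exchangeable working correlation was used, so that small clinics are over-weighted despite the 1/(clinic size) weights. The Protocol never mentions that structure, and reporting an ICC does not imply it.

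It is also fair to say that the choice among corrections is partly preference: several come close to 5%.

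**Conclusion.** The concern holds in conditional form. If the robust variance is the ordinary sandwich, the reference is normal and Health Center enters as seven indicators, the two-sided type I error is about 12-15% against a stated 5%. Standard errors are then about 77-84% of what they should be (√0.60 to √0.70). A t reference without a variance correction does not cure it. The size agrees across a closed form, a normal analogue and logistic simulations under two data models. What is inferred, not documented, is that no correction was applied.

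**What to change.** In section 2.4.1 keep the model, weights and effect estimate, and state how the p-value and interval are obtained. Either of these would do:
- a small-sample-corrected sandwich, for example Kauermann-Carroll, with t on 17 df (26 − 8 − 1), which gives about 5-7% in simulation at ICCs of .03-.05;
- a re-randomization test that permutes arms within Health Center, matching the stratified design. With near-equal splits held fixed there are 2×3×3×6×20×2×6×2 = 51,840 arrangements, ample for a test at 0.05.

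Apply the same to any CRC screening and to the GEE sensitivity models. Because the text reports the model as fitted and its ICC as known, label this as a later change and show the result with and without it. If a correction was already used, naming it is enough.

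As a minor clarification, separate from the error, state working independence so that the weights give each clinic the equal weight the plan intends.

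The cost is a few sentences, some reprogramming and less favourable inference. By the approximation above, a corrected interval is about √(26/17) × 2.110/1.960 = 1.33 times as wide as an uncorrected z interval, and p-values rise accordingly.
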